5.2 Sample Size and Power Calculation

We will enroll 40 participants undergoing autologous HCT for MM at MCW. Accounting for study attrition and beta-blocker intolerance, we aim to have 30 patients with a complete set of prenylation data. A targeted final sample of 15 participants in the intervention group will be sufficient for Western blot analysis. This sample size is established for the purpose of the parent study and should be sufficient to describe prenylation.

5.3 Analysis of Primary Endpoints

5.3.1 Rap1 prenylation by beta-blocker exposure

Western blotting on the cytosolic and membrane fractions of isolated PBMCs will determine the distribution of Rap1 in the different fractions as well as the status of Rap1 prenylation in the cells exposed vs. not exposed to beta-blocker therapy. The statistical difference between cells from patients exposed to beta-blocker therapy (intervention arm) vs. those not exposed to beta-blocker therapy (control arm) will be determined by repeated-measures of analysis of variance (ANOVA) individually at the two blood assessment time points on beta-blocker therapy (Day -2, and Day +30). Baseline Rap1 prenylation will also be assessed by the first blood draw and may be compared to later time points. Patients will be included in final analyses if and only if they have been adherent to the study drug during the designated time period as described in the parent protocol.

References

2. Williams CL. A new signaling paradigm to control the prenylation and trafficking of small GTPases. *Cell Cycle*. 2013;12(18):2933-2934.
4. Linden J. Adenosine promotes tumor metastasis. *Sci Signal*. 2013;6(277):pe20.

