2.1 Primary Objective

The primary objective of this ancillary study is to explore whether beta-blocker administration will promote prenylation and membrane localization of Rap1 in peripheral blood mononuclear cells (PBMCs).

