3.0 STUDY ENDPOINTS

Western blotting on the cytosolic and membrane fractions of isolated PBMCs will determine the distribution of Rap1 in the different fractions as well as the status of Rap1 prenylation in the cells exposed vs. not exposed to beta-blocker therapy.

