4.0 ENROLLMENT PROCEDURES

4.1 Patient Enrollment

Patients will be approached for this study during the pre-transplant evaluation phase. Transplant physicians will evaluate the patient eligibility onto the parent study and this ancillary study. Eligible patients willing to participate in the trial will sign an MCW IRB approved informed consent form. A Clinical Trials Office CRC will record the documentation of patient consent and proceed with registration procedures. All source documents that support eligibility including a signed informed consent/HIPAA and signed eligibility checklist, will be available, reviewed and eligibility verified. At the point of registration, a member of the study team will register the patient in the electronic database, including demographics, consent and on-study information. The patient will be assigned a unique sequence number for the study. The principal investigator (PI) of the study, [name], will be notified prior to enrollment. If at any point in time a patient wishes to withdraw from the study, they may notify [name] verbally or in writing. There will be no further data collection for participants who elect to withdraw from the study.

Target enrollment is 40 (20 per group) and includes patients undergoing autologous HCT for MM at MCW. Half of the participants in the parent study will be randomized via permuted block assignment with random block sizes to receive propranolol upon study entry. Informed consent will be obtained to access participants' full medical records to ascertain relevant demographic and medical data as outlined in Section 4.2. The patient must have signed informed consent prior to registration on both studies. Due to the pilot and feasibility nature of this study, the need to monitor response to prophylactic beta-

blocker usage in a medically ill population, as well as the objective nature of Western blot analysis, this pilot study will not be blinded. Patients will be enrolled by Day -7.. Total study duration will be up to 7 weeks for participants assigned to the intervention group (1 week pre-transplant through 6 weeks post-transplant) and 5 weeks for those in the control arm (1 week pre-transplant through 4 weeks post-transplant). Additional clinical information will be collected for 100 days post-transplant as identified in section 3.2.2.2.

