4.4 Specimen Collection

The Cancer Center Lab will draw one tube of blood to be stored in 8 mL BD Vacutainer CPT tubes at three study time points as described in Table 4.7b. These time points include baseline (Day -7), Day -2 (immediately prior to transplant, central line placement, or administration of any conditioning regimen), and Day +28. Blood will be drawn at one of two locations: in the hospital (if participants are immediately post-transplant and/or still or re-hospitalized) or in the transplant clinic during their regular visits. These 8 mL BD Vacutainer CPT tubes will be transferred to [name] lab at MCW for Western blot analysis. Before being transferred they will be assigned a dummy ID that will be the sole identifier of the samples. The linked identifiers will be stored on a secure computer network through the Clinical Trials Office under the PI's name.

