5.1.2 Primary Endpoint

The primary endpoint is Day +28 (4 weeks) following HCT for MM, with intervention arm patients followed for an additional 1-2 weeks until they are weaned from beta-blocker therapy.

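### The between-arm Rap1 test leaves out the scheduled baseline sample; using it as an ANCOVA covariate would cost very little, provided that the draw precedes study drug

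*Combined protocol and SAP*

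**What the plan says.** The primary objective (Section 2.1) is to explore whether beta-blocker administration "will promote prenylation and membrane localization of Rap1" in PBMCs. Section 3.0 takes as endpoints the distribution of Rap1 between cytosolic and membrane fractions, "as well as the status of Rap1 prenylation in the cells exposed vs. not exposed to beta-blocker therapy". Section 5.1.2 fixes the time: "The primary endpoint is Day +28 (4 weeks) following HCT for MM".

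Blood is drawn three times. Section 4.4 states "These time points include baseline (Day -7), Day -2" and then Day +28, and Table 4.7a puts baseline at Day -7 ± 2 days.

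Section 5.3.1 gives the only between-arm test. The difference "will be determined by repeated-measures of analysis of variance (ANOVA) individually at the two blood assessment time points on beta-blocker therapy", and the two points named are Day -2 and Day +30. Baseline has a separate sentence: "Baseline Rap1 prenylation will also be assessed by the first blood draw and may be compared to later time points". No section names a covariate, a change-from-baseline outcome or a model that contains baseline.

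Section 5.3.1 also limits the final analyses to patients who adhered to study drug. Section 5.2 says "we aim to have 30 patients with a complete set of prenylation data", with 15 of them in the intervention group, and gives no power, alpha, effect size or SD.

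**The concern.** The study draws and blots a baseline sample from every patient but gives the result no defined part in the comparison of arms. With about 30 evaluable patients, two things are at stake.

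The first is precision. If baseline Rap1 predicts later Rap1, leaving it out widens the interval and leaves chance baseline differences uncorrected.

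The second is the open choice. The optional wording allows no adjustment, a change score or a covariate, and these can give different estimates and intervals from the same data. Section 4.1 says that the study is not blinded, so the choice is best settled before results are seen.

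The ANOVA sentence does not settle it. A repeated-measures analysis run separately at each draw needs a within-patient factor, and none is named. It could be fraction (cytosolic or membrane). Whatever the factor, the test covers only the two later draws.

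**Working it through.** **The plan's own figures.** There is no power calculation to reproduce. Going from 40 enrolled to 30 complete implies 1 − 30/40 = 25% loss.

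**Inputs.** From Section 5.2: 15 evaluable in the intervention group and 30 in all, so 30 − 15 = 15 controls. Assumed, because the documents are silent: true effect 0.8 follow-up SD, two-sided alpha 0.05, equal baseline and follow-up SDs, and baseline to follow-up correlation r of 0, 0.3, 0.5 or 0.7.

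**Unadjusted test at one draw.** SE = √(2/15) = 0.365 SD. Noncentrality = 0.8/0.365 = 2.19, with 28 df and critical t 2.048. Power is 56.2% and the mean 95% CI half-width is 0.74 SD. If fraction is the within-patient factor, the arm-by-fraction test with two fractions is a two-group test on each patient's membrane-minus-cytosol difference. The same arithmetic then applies to that difference.

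**ANCOVA on baseline.** Variance ≈ (1 − r²) × (2/15) × (1 + 1/26), with 27 df and critical t 2.052. The factor 1 + 1/26 = 1.038 is the average price of chance baseline imbalance. Noncentrality is 2.15, 2.25, 2.48 and 3.01. The powers below average over the imbalance, and simulation agrees.

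**Change score.** SD = √(2(1 − r)) = 1.41, 1.18, 1.00 and 0.77. Noncentrality = 0.8/(SD × 0.365) = 1.55, 1.85, 2.19 and 2.83, with 28 df.

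| r | Unadjusted power | ANCOVA power | Change-score power | ANCOVA mean half-width (SD) |
|---|---|---|---|---|
| 0 | 56.2% | 54.6% | 32.2% | 0.76 |
| 0.3 | 56.2% | 58.5% | 43.2% | 0.72 |
| 0.5 | 56.2% | 66.8% | 56.2% | 0.65 |
| 0.7 | 56.2% | 82.7% | 77.9% | 0.54 |

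**Cost and break-even.** The loss at r = 0 is 56.2 − 54.6 = 1.6 points. Ignoring the lost degree of freedom, ANCOVA breaks even when (1 − r²) × 1.038 = 1, that is r = 0.19; the full calculation also gives 0.19.

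**Unequal SDs.** Let k be baseline SD divided by follow-up SD. The change score loses to the unadjusted test whenever r < k/2. Its power is 47, 58, 69 and 81% at k = 0.5, and 22, 28, 36 and 51% at k = 1.5. ANCOVA does not depend on k. In this grid the change score beats ANCOVA only at k = 0.5 and r = 0.5 (69 against 67%), where the slope of follow-up on baseline, r/k, is exactly 1.

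**Other effect sizes.** At 0.5 SD, power is 26% unadjusted and 26, 28, 32 and 44% with ANCOVA. At 1.0 SD it is 75% unadjusted and 74, 78, 85 and 95% with ANCOVA.

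**Chance imbalance.** In an intact randomized sample of 15 per arm, the baseline difference has SD 0.365 and exceeds 0.5 SD in 17% of trials. An imbalance of 0.5 SD shifts the unadjusted follow-up difference by r × 0.5 = 0.15, 0.25 or 0.35 SD at r = 0.3, 0.5 or 0.7.

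**If baseline were taken after the first dose.** Suppose, as an illustration, that baseline already carried half of a 0.8 SD effect (0.4 SD). ANCOVA would then estimate 0.8 − r × 0.4 = 0.68, 0.60 or 0.52 SD at r = 0.3, 0.5 or 0.7. Pre-dose timing is therefore a condition of the fix.

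**The case against.** The strongest case against is that this is an exploratory ancillary study. Its sample size was set for the parent study, it claims no power, and an unadjusted randomized comparison is legitimate. On that view, preferring ANCOVA is a choice about efficiency, and optional wording is normal for a pilot. This stands, and it sets the severity. A reader might infer that the planned test is invalid or the trial underpowered; the documents support neither.

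A reader might also infer that the ANOVA is simply a two-sample test on one value per patient. The documents do not say so: each draw is blotted in two fractions, so a repeated-measures analysis at a single draw can be coherent. What remains is that the factor is unnamed and baseline is outside the test either way.

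The gain is unknown, and this stands too. Conditioning and transplant fall between baseline and Day +28, so a high correlation cannot be presumed. Below about 0.2 there is a slight loss.

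The imbalance figures assume an intact randomized sample, whereas the plan analyses adherent patients only. Imbalance there need not be due to chance alone, and adjustment for baseline does not remove that selection.

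Finally, the low cost depends on a pre-dose baseline. Section 5.3.1 implies one by describing only the two later draws as on therapy. Section 4.1, however, has patients randomized "to receive propranolol upon study entry" with enrollment by Day -7, while baseline may fall two days after Day -7. A reader might infer that baseline is contaminated by drug. The documents do not show that, but they leave the order unstated.

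The Day +30 label in Section 5.3.1 is not evidence of a different endpoint, since it lies within the 28 ± 2 day window.

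**Conclusion.** The point holds as a low-severity improvement in precision. Baseline Rap1 is collected but has no set role in the comparison of arms. Under the stated assumptions, ANCOVA gives up at most about 1.6 points of power and 0.015 SD of interval half-width if the correlation is 0. It gains about 2, 11 and 27 points at 0.3, 0.5 and 0.7. With equal SDs a change score gives up 24 points at 0 and 13 at 0.3, so leaving the choice open carries more risk than the covariate does. No particular gain can be claimed, because the documents give no correlation, SD or effect size. The conclusion requires a baseline drawn before study drug and does not extend to the selection made by the adherence rule.

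**What to change.** First, confirm whether the baseline draw precedes the first dose of study drug, and reconcile Sections 4.1, 4.4 and 5.3.1 and Table 4.7a on this. If it does not, baseline should not be used as the covariate.

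If it does, replace the ANOVA sentence in Section 5.3.1 with wording such as: *For each Rap1 measure (for example the membrane share of Rap1, or prenylation status), the arms are compared at Day +28, and likewise at Day -2, by ANCOVA with arm and the baseline value of that measure, reporting the difference with a 95% CI.* Replace the optional baseline sentence with: *Baseline is the covariate in this model; change scores are descriptive only.*

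The cost is a few sentences and one degree of freedom. The draw and blot are already scheduled. A patient without a baseline value would drop out of a complete-case ANCOVA, but Section 5.2 already aims for complete prenylation data.

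### Section 5.3.1 plans a repeated-measures ANOVA at each visit separately but names neither the repeated measurement nor the deciding term; a baseline-adjusted comparison of the membrane share would fit the objective better.

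*Combined protocol and SAP*

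**What the plan says.** The primary objective (Section 2.1) is to explore whether beta-blockade "will promote prenylation and membrane localization of Rap1" in PBMCs. Section 3.0 gives the readout: Western blotting of the cytosolic and membrane fractions "will determine the distribution of Rap1 in the different fractions", together with prenylation status. Section 5.3.1 repeats that readout and then gives the only analysis of it. The contrast is "The statistical difference between cells from patients exposed to beta-blocker therapy (intervention arm) vs. those not exposed to beta-blocker therapy (control arm"), and the method is "repeated-measures of analysis of variance (ANOVA) individually at the two blood assessment time points" on therapy.

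On baseline, the same section says: "Baseline Rap1 prenylation will also be assessed by the first blood draw and may be compared to later time points".

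Section 4.4 and Table 4.7b provide one tube of blood at each of three time points: baseline, Day -2 and Day +28. Section 5.2 plans 40 enrolled and 30 with complete prenylation data, 15 of them in the intervention group. No section gives a dependent variable with its scale, a within-patient factor, a model term to be tested, a significance level, an effect size or a standard deviation.

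**The concern.** A repeated-measures ANOVA needs at least two measurements per patient within the model. Running it separately at each visit takes time out, and one tube per visit leaves nothing that the plan identifies as repeated. The two fractions of that tube are the obvious candidate.

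If fraction is the repeated factor, the model has two terms involving arm, and they answer different questions. The arm main effect compares each patient's average over the two fractions. The arm-by-fraction interaction compares membrane minus cytosol. The objective concerns where Rap1 is located, which is the second question, yet the only contrast written down is intervention against control, with no interaction or membrane share mentioned. An analyst who took the main effect could miss relocation, or report a rise in both fractions as a positive result. Because the study is unblinded (Section 4.1), the choice of term is better fixed before the blots are analysed.

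**Working it through.** **1. The plan's own figure.** 30 complete out of 40 enrolled implies a loss of 1 - 30/40 = 25%, and 30/0.75 = 40. The figures agree with each other. The 25% is implied rather than stated, and there is no power figure to reproduce. With 15 of the 30 in the intervention group, 30 - 15 = 15 controls remain.

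**2. Assumptions.** 15 per arm, two-sided alpha 0.05, SD 1 in each fraction, correlation r between a patient's two fractions. Only the 15 comes from the documents.

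**3. What each term tests.** With two fractions per patient and two arms:
- the arm main-effect F equals t² on the patient mean (C + M)/2;
- the arm-by-fraction F equals t² on the patient difference M - C.

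Both identities were checked against explicit sums of squares on a simulated data set (0.108 = 0.108 and 2.412 = 2.412).

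**4. Equal and opposite shifts** (cytosol down by s, membrane up by s). The mean changes by (-s + s)/2 = 0. The difference changes by 2s, with SD √(2(1 - r)). Rejection rates from 20,000 simulated trials per setting:

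| r | main effect, s = 0.5 | interaction, s = 0.5 | main effect, s = 1 | interaction, s = 1 |
|---|---|---|---|---|
| -0.5 | 4.9% | 33% | 4.5% | 86% |
| 0 | 5.4% | 47% | 4.9% | 96% |
| 0.3 | 5.1% | 61% | 4.9% | 99% |
| 0.5 | 4.8% | 75% | 5.0% | 99.9% |
| 0.8 | 4.8% | 99% | 4.9% | 100% |

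**5. The reverse case.** A rise of 1 SD in both fractions with no relocation makes the main effect reject 96% of the time (r = 0) or 86% (r = 0.5), while the interaction stays at about 5%.

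**6. Constant total, analysed on logs.** Here the cancellation is not exact. Suppose the membrane share goes from 20% to 40% with total Rap1 fixed.
- Membrane: ln(0.40/0.20) = 0.693. Cytosol: ln(0.60/0.80) = -0.288.
- Change in mean: (0.693 - 0.288)/2 = 0.203. Change in difference: 0.693 + 0.288 = 0.981.
- Set the change in difference to 1.06 SD, which gives 80% power for the interaction at 15 per arm. Then the SD of the difference is 0.981/1.06 = 0.925.
- SD of the mean = 0.925 × ½ × √((1 + r)/(1 - r)): 0.463 at r = 0 and 1.101 at r = 0.7.
- Standardised main effect: 0.203/0.463 = 0.44 and 0.203/1.101 = 0.18. The two-sample t-test then rejects 21% and 8% of the time.

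**7. Percent-of-total scale.** The two fractions sum to 100, so every patient's mean is 50 and its variance is zero. The arm main effect cannot be tested at all; the membrane share carries all the information.

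**The case against.** A reader might infer that the plan tests total Rap1 and cannot detect movement to the membrane. The documents do not support that, for four reasons.

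- The repeated factor is an inference. The sentence could describe a model across visits with arm comparisons reported at each of the two on-treatment visits. Prenylated versus unprenylated form, or replicate blots, are also possible.
- The plan does not select the arm main effect. The sentence before the test says that blotting "will determine the distribution of Rap1 in the different fractions as well as the status of Rap1 prenylation", so the difference between arms can fairly be read as a difference in distribution. In a two-fraction ANOVA that is the interaction, which the same model contains and which responds to the shift. Total Rap1 is nowhere named as an endpoint.
- The average of the fractions reflects total Rap1 only if both are quantified on a common input scale, which is not stated. On logs, the main effect retains some sensitivity (step 6).
- Prenylation status is a separate readout, so a poor localization test would not by itself decide the whole objective.

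It can also be said that this is an exploratory pilot whose sample size is meant to describe prenylation. All of these points stand, and they limit the finding. They do not remove it: a visit-based model would still leave the dependent variable unnamed, prenylated versus unprenylated form would raise the same choice of term, and a single membrane share per patient would need no repeated-measures model at one visit.

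**Conclusion.** The concern holds in a limited form. The stated method fits the redistribution objective poorly, because at a single visit it has no stated repeated measurement and no named deciding term, and baseline enters only as an optional comparison. On the most natural reading, the result depends heavily on which term is read: about 5% rejection (about 8-21% in the constant-total log example) for the arm main effect, against 33-99% for arm-by-fraction at a 0.5 SD shift in each fraction and 86-100% at 1 SD. These rates assume 15 per arm, two-sided 5%, and correlations of -0.5 to 0.8 (0 to 0.7 in the log example). They show how much turns on the choice and do not estimate this trial's power. Nothing shows that the sponsor intends the insensitive term. The change is worth making because a better-matched analysis is available from data already planned, at almost no cost.

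**What to change.** In Section 5.3.1, replace the per-visit repeated-measures ANOVA with the following.

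- **Outcome:** for each patient and visit, membrane Rap1 / (membrane + cytosolic Rap1), with both fractions quantified on a common input scale.
- **Analysis:** at each on-treatment visit, compare arms by ANCOVA with the patient's baseline share as covariate.
- **Prenylation status:** the same analysis on the prenylated share of total Rap1, adjusted for its baseline value.
- **If the two-fraction ANOVA is kept:** state that fraction is the within-patient factor and that arm-by-fraction is the test of interest.

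In the same edit, reconcile the analysis label Day +30 with the scheduled draw at Day +28 (28 ± 2 days in Table 4.7a). The cost is a few sentences of analysis text. The three blood draws, including baseline, are already scheduled, so no extra samples, visits or patients are needed; the laboratory only has to record both fractions on the same input scale.

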1.2 Beta-blockade and cancer

Retrospective epidemiologic studies have linked the use of beta-blockers to reduced rates of progression for several solid tumors.⁵⁻⁹ Recently, a retrospective case-control study of MM patients identified that concurrent use of any beta-blocker is associated with more favorable 5-year overall and disease-specific survival.¹⁰ Preclinical pharmacologic and biomarker studies in animals are now laying the groundwork for translation of beta-blockade as a novel adjuvant to existing therapeutic strategies in clinical oncology, linking the use of beta-adrenergic antagonists (beta-blockers) with reduced disease progression in humans.^{5-9, 11-18} Further, propranolol, a non-selective beta-adrenergic receptor blocker, has apoptotic and anti-proliferative effects on multiple myeloma (MM) cells.¹⁹ Propranolol is the most studied nonselective beta-blocker;²⁰ this, along with its safe side effect profile, cost-effectiveness, and efficacy *in vitro* in preventing tumor progression as compared to selective beta-antagonists^{16, 21, 22} make it our preferred beta-blocker for use in the current proposal. Propranolol does not have any significant drug interactions with the more common antineoplastic (melphalan) and infection-related drugs utilized to treat MM.

The first 30 days following autologous hematopoietic stem cell transplantation (HCT) generally constitute the time period around transplantation of greatest psychological and physiological stress and inflammatory processes.^{23, 24} Psychosocial stress gradually improves over time with a return to pre-transplant psychosocial functioning by about one year post-transplant.^{25, 26} Therefore, it follows that the first 30 days may also be the time

period of highest beta-adrenergic signaling due to increased stress response. Further, data from mouse models have demonstrated that beta-blockade with propranolol 8 days prior to exogenous stress exposure is effective in blocking beta-adrenergic signaling at the tumor level.¹⁷ Tumor metastasis in mouse models is increased 30-fold as compared to the control group after 20 days of exposure to chronic stress.²⁷

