1.4 Rationale

This study will explore whether prenylation of Rap1 - recently identified as being under beta-adrenergic control - may be affected by beta-blocker use. Further, the proposed study addresses a major goal of the MCW Cancer Center; it promotes collaborative interactions between basic science researchers and clinicians at the Medical College. The proposed investigation of Rap1 prenylation will enhance the translational significance of [name] studies of Rap1 and may lead to future clinical trials of beta-blockers as novel therapeutic regulators of Rap1 in cancer.

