4.5 Rap1 prenylation

Peripheral blood mononuclear cells (PBMCs) will be isolated from the whole blood samples collected from patients at the three designated time points (Baseline, Day -2, and Day +28). Members of [name] laboratory (Professor, Pharmacology and Toxicology, MCW) will conduct western blotting on the cytosolic and membrane fractions of isolated PBMCs to determine the distribution of Rap1 in the different fractions, and the status of Rap1 prenylation in the cells.

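### The baseline Rap1 draw is left out of the between-arm test and has no specified role; adjust the arm comparison for it and keep within-arm changes descriptive

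*Combined protocol and SAP*

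**What the plan says.** **Main analysis.** Section 5.3.1 contrasts patients on beta-blocker therapy "vs. those not exposed to beta-blocker therapy (control arm) will be determined by repeated-measures of analysis of variance (ANOVA"), applied "individually at the two blood assessment time points on beta-blocker therapy (Day -2, and Day +30"). Baseline is named neither as a covariate nor as a level of that analysis.

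**Baseline.** The next sentence of section 5.3.1 is the only one on analysing it: "Baseline Rap1 prenylation will also be assessed by the first blood draw and may be compared to later time points". The wording is optional and does not say whether the comparison is within an arm, pooled, or between arms.

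**Design.** Section 4.1 provides a concurrent randomised control: "Half of the participants in the parent study will be randomized via permuted block assignment with random block sizes to receive propranolol upon study entry". Section 4.5 has cells "isolated from the whole blood samples collected from patients at the three designated time points (Baseline, Day -2, and Day +28"), with no restriction by arm. The footnote to Table 4.7a places the Day -2 draw before conditioning, so only the last draw follows conditioning and transplant.

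**Sample size.** Section 5.2 enrols 40, aims for 30 with complete prenylation data, and adds: "A targeted final sample of 15 participants in the intervention group will be sufficient for Western blot analysis".

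**Biology.** Section 1.1 says that receptor activation inhibits Rap1 prenylation, and section 1.4 describes this prenylation as "recently identified as being under beta-adrenergic control". Section 1.2 calls the first 30 days after transplant "the time period around transplantation of greatest psychological and physiological stress and inflammatory processes", and infers that they may also be the time of highest beta-adrenergic signalling.

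**Timing.** Section 5.3.1 refers to Day +30. Sections 4.4, 4.5 and 5.1.2 refer to Day +28, and Table 4.7a allows 28 ± 2 days.

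**The concern.** A pre-treatment value of the outcome is usually among the best predictors of the later value. Leaving it out of the randomised comparison costs precision, which is scarce with about 15 evaluable patients per arm.

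The loose sentence also leaves room for an analysis that cannot answer the objective. Between baseline and Day +28 every patient receives conditioning and a transplant, and the protocol itself expects stress signalling to be high in that period. A change within the propranolol arm is therefore the drug effect plus whatever transplant does. The study is unblinded and the sentence stands under the analysis of primary endpoints, so a choice made after seeing the data would carry little weight. At stake is whether the pilot's one biological question is answered from the randomised contrast, with all the information collected, or from a before-after change that cannot be interpreted alone.

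**Working it through.** **1. The plan's own figures.** Section 5.2 implies 25% loss: 40 × 0.75 = 30 overall and 20 × 0.75 = 15 in the intervention arm, which leaves 30 − 15 = 15 controls. The arithmetic is consistent, but the 25% is inferred from the two totals and not stated. No alpha, power, effect size, SD or correlation is given, so there is no power figure to reproduce.

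Assumed from here on: n = 15 per arm, SD = 1, two-sided 5%, and correlation r between baseline and later value of 0.3, 0.5 or 0.7.

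**2. What baseline adds to the between-arm test (effect 0.8 SD).**
- Later values only: noncentrality = 0.8 × √(15/2) = 2.19; 28 df; critical t = 2.05; power 56%.
- Baseline as covariate: the residual variance is multiplied by 1 − r², so the noncentrality becomes 2.19 / √(1 − r²), with 27 df.
- Change from baseline: variance is 2(1 − r).

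| r | 1 − r² | Noncentrality, adjusted | Power, adjusted | Detectable at 80% power, adjusted | Detectable at 80% power, change score |
|---|---|---|---|---|---|
| 0.3 | 0.91 | 2.30 | 60% | 1.01 SD | 1.25 SD |
| 0.5 | 0.75 | 2.53 | 68% | 0.92 SD | 1.06 SD |
| 0.7 | 0.51 | 3.07 | 84% | 0.76 SD | 0.82 SD |

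Without baseline the detectable difference is 1.06 SD. An unadjusted change score is worse than that at r = 0.3 and no better at r = 0.5. Baseline should therefore enter as a covariate rather than by subtraction.

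**3. What a within-arm reading would measure.** Let D be the drug effect and S the transplant-related shift. The expected change is D + S on propranolol and S on control. The difference between arms is D; the within-arm change is D only if S = 0.

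For a paired test with D = 0, noncentrality = S × √15 / √(2(1 − r)), with 14 df. At r = 0.5 the divisor is 1, so S = 0.25, 0.5 and 0.75 SD give 0.97, 1.94 and 2.90.

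| Size of S | Significant, r = 0.3 | r = 0.5 | r = 0.7 |
|---|---|---|---|
| 0.25 SD | 12% | 15% | 21% |
| 0.5 SD | 33% | 44% | 64% |
| 0.75 SD | 63% | 77% | 94% |

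A 20,000-run simulation at S = 0.5 and r = 0.5 gave 44% within the arm, 5.1% for between-arm change and 4.9% for between-arm later values.

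**4. Direction.** These percentages count significant changes either way. In the protocol's model, activation inhibits prenylation, so stress gives a negative S, while propranolol is expected to raise prenylation. With S = −0.25, −0.5 and −0.75 SD and r = 0.5, a significant increase occurs in about 0.2%, 0.01% and under 0.01% of trials. Almost all the significant results are decreases.

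**5. Masking.** Take D = 0.9 SD, S = −0.5 SD and r = 0.5. The within-arm change is 0.9 − 0.5 = 0.4 SD, with power 30%, against 90% if there were no shift. For the same D, the between-arm change has 66% power and the baseline-adjusted comparison 78%, whatever the common shift.

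**The case against.** The strongest reply is that the plan proposes no uncontrolled test. The baseline sentence names no arm and no p-value, and a between-arm comparison of change fits it equally well. The inference about the drug is assigned, one sentence earlier, to intervention against control in a randomised study. A pilot that sets out to explore may leave a secondary remark open. All of this stands: the defect is missing specification, not a stated invalid analysis.

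A reader might make three stronger inferences that the documents do not support:
- **That transplant confounds the main result.** A shift common to both arms cancels in the named between-arm test, as the simulated 4.9% shows. That says nothing about other features of the analysis, such as its restriction to adherent patients.
- **That section 5.2 endorses a single-arm test.** It first asks for 30 complete patients across both arms, and the figure of 15 concerns adequacy for Western blotting.
- **That stress would produce a false propranolol effect.** This joins two statements, one hedged with 'may', and the protocol's direction points the other way. A false increase needs an upward shift from some other source, about which the documents say nothing.

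The reply leaves one thing unanswered. Baseline is scheduled for everyone, yet the plan does not use it in the comparison that matters.

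**Conclusion.** The point holds as a gap in specification with a cheap improvement available. Section 5.3.1 keeps baseline out of the randomised comparison and leaves its use undefined, which permits a within-arm baseline-to-Day +28 reading that cannot isolate propranolol. If that reading were used, masking a true increase is the likelier error on the protocol's own reasoning.

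The gain from adjustment, for an assumed 0.8 SD effect with 15 per arm, is 4, 12 or 28 percentage points of power (56% to 60%, 68% or 84%) at r = 0.3, 0.5 or 0.7. It is small if baseline predicts poorly and substantial if it predicts well. SD, effect, correlation, shift and significance level are all assumptions, so the figures show the order of magnitude and do not forecast this trial's power.

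**What to change.** Replace the baseline sentence in section 5.3.1 with:

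> The between-arm comparison at each later draw is adjusted for baseline Rap1 prenylation (ANCOVA, or an equivalent repeated-measures model with baseline as covariate). Within-arm changes from baseline are shown descriptively for both arms, without p-values, and are not evidence for the primary objective.

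In the same edit, reconcile Day +30 in section 5.3.1 with Day +28 in sections 4.4, 4.5 and 5.1.2 and Table 4.7a. Make this one change together with any other revision of how baseline is handled.

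The cost is a short wording change and one degree of freedom; no extra blood draw is needed. The small downside is that within-arm tests can no longer serve as evidence. They look more powerful when there is no time shift (90% against 66% to 78% for 0.9 SD at r = 0.5), but that advantage depends on an assumption the trial cannot verify from one arm.
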